2.3.1. Primary Endpoint

The primary endpoint of the trial is overall disease control (SD, CR or PR) as determined by radiographic measurements. All subjects in Treatment Period 1 will undergo radiographic imaging (CT or MRI scan of chest, abdomen and pelvis) prior to treatment, after 12 weeks of progestin monotherapy (at Visit -1), and if disease control is maintained, again after an additional 12 weeks of progestin monotherapy (at Visit TP1-EXT). During Treatment Period 2, subjects will undergo a CT or MRI scan at 12-week intervals. Subjects may also be assessed at any point when the Investigator determines radiographic imaging is indicated. Radiographic disease progression and responses will be defined using RECIST 1.1 criteria as detailed in Section 5.5, and the ODCR will be determined as described in Section 7.4.

2.3.2. Secondary Endpoints

The secondary endpoints of the trial include safety and other efficacy parameters. As before, radiographic imaging will be used to assess the ORR, PFS, duration of stable disease, and OS. A more detailed description of how these will be calculated is included in Section 7.4. Safety will be assessed as described in Sections 5.7 and 5.9.

3. STUDY POPULATION

3.1. Selection of Study Population

This study will enroll subjects with recurrent or persistent endometrial cancer.

3.2. Informed Consent

Before any study-related screening procedure is performed, each potential subject will be informed of the study's objectives and requirements. The Investigator or his/her designee will explain the study fully to the subject using the Informed Consent Form (or Patient Information Sheet, as applicable in some countries). If the subject is willing to participate in the study, written informed consent will be requested after sufficient time to consider participation and the opportunity to ask further questions has been

given. The Informed Consent Form will be signed and personally dated by both the subject and the person obtaining the consent. The person obtaining consent must be the Investigator or his/her designee who is also medically qualified. The subject will be provided a copy of the signed and dated Informed Consent Form. The original signed and dated Informed Consent Form will be retained with the source documents.

3.3. Screening

Following the receipt of informed consent, potential subjects will be assigned a subject identification number and undergo screening procedures to determine eligibility for the study. Screening procedures will be conducted according to the Visit and Assessment Schedule described in Section 5.4.

3.4. Inclusion Criteria

1. Female patients 18 years of age or older;
2. Histologically confirmed serous carcinoma or endometrioid type of endometrial carcinoma (histological documentation of recurrence is not required);
3. Recurrent or persistent progressive disease which is refractory to curative therapy or established treatments and cannot be treated with surgery or radiotherapy;
4. Measurable disease, as defined by RECIST 1.1 criteria;
5. At least one “target lesion” to be used to assess response, as defined by RECIST 1.1 criteria. Tumors within a previously irradiated field will be designated as “non-target” lesions unless previous progression is documented;
6. Availability of archived tumor tissue sample that can be used for assessment of PrR status by the central laboratory;
7. GOG performance status 0-2 (refer to Table 9 under Section 5.5.3);
8. eGFR \geq 50 mL/min;
9. Total bilirubin \leq 2.5 times upper limit of normal (ULN);
10. AST \leq 2.5 ULN (\leq 5 times ULN for patients with liver metastases);
11. Alkaline phosphatase \leq 2.5 ULN (\leq 5 times ULN for patients with liver metastases);
12. Albumin \geq 3.0 mg/dL;
13. Ability to take oral medication
14. Patients able to understand the nature of the study and who are willing to give written informed consent;
15. *And or Treatment Period 2 only*, Patients participating in Treatment Period 1 must have had disease progression after receiving at least 4 weeks of progestin therapy or 2) Patients must be determined as PrR negative status at Screening.

Waivers to the inclusion criteria will **NOT** be allowed.

3.5. Exclusion Criteria

1. Mixed histology of the tumor or evidence of tumor histology other than serous carcinoma or endometrioid type of endometrial carcinoma;
2. Concurrent systemic corticosteroid therapy;
3. Concurrent oral contraceptive use / Women of childbearing potential not using highly effective means of contraception;
4. Pregnancy confirmed by pregnancy test / Lactating women (for women of childbearing potential);
5. Prior therapy with hormonal progestin agents;
6. Patients who are candidates for treatment with standard chemotherapy agents (there is no limit to the number of lines of prior chemotherapy);
7. History of blood clot;
8. History of known bleeding disorder (i.e. disseminated intravascular coagulation or clotting factor deficiency);
9. Major surgery within 4 weeks prior to the start of the study;
10. Patients with clinically significant illnesses which, according to the Investigator, could compromise participation in the study;
11. History of other clinically active malignancies within 5 years, except for carcinoma in situ of the cervix, basal cell carcinoma, or squamous carcinoma of the skin.
12. Known hypersensitivity or idiosyncratic reaction to any of the study drugs (Sodium Cridanimod, megestrol acetate, lidocaine) and excipients;
13. Patients with known brain metastases;
14. Patients currently receiving any other investigational agents;
15. Patients currently receiving any other anticancer therapies;
16. Participation in any other clinical study within the last 4 weeks prior to the start of the study;

Waivers to the exclusion criteria will **NOT** be allowed.

3.6. Discontinuation Criteria for Individual Subjects

Treatment may continue until one of the following criteria applies:

- Disease progression (during Treatment Period 2 only),
- A Grade 3 or higher AE (according to NCI-CTCAE Version 4 criteria) is observed and is determined to be related to either the Sodium Cridanimod or progestin therapy.
- Concurrent illness that prevents further administration of treatment,
- Unacceptable AE(s),

- Patient decides to withdraw from the study, or
- General or specific changes in the patient's condition render the patient unacceptable for further treatment in the judgment of the Investigator.

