5.1.2. Dose Modifications

There will be no allowed modifications to the dosage, including dose reduction, of either megestrol acetate or Sodium Cridanimod during the trial.

If injection of Sodium Cridanimod was not administered on the scheduled dosing date, this can be done during the next two days but not later than 1 day before the next scheduled dose. The subsequent injection of Sodium Cridanimod should be given according to the study drug administration schedule.

If a subject misses a dose of megestrol acetate, the next dose should be taken at the regularly scheduled time.

Sodium Cridanimod and megestrol acetate combination therapy should be discontinued if an AE of Grade 3 or higher (according to NCI-CTCAE Version 4 criteria) is observed and determined to be potentially related to either medication. When combination treatment is discontinued, both Sodium Cridanimod and megestrol acetate are to be discontinued. Monotherapy in Treatment Period 2 is not permitted. The treatment will not be re-started and the subject will be withdrawn from Treatment Period 2. The subject will then enter the Follow-up Period as described in Section 5.1.4.

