5.9.3. Criteria for Causal Relationship

Table 14. The causality of each AE should be assessed using one of the following terms:

Causal Relationship* to the Study Drug	Criteria for Causal Relationship
Related	AE occurring in a plausible time relationship to drug administration, and which cannot be explained by concurrent disease or other drugs or chemicals.
Possibly Related	AE occurring with a reasonable time sequence to administration of the drug, unlikely to be attributed to concurrent disease or other drugs or chemicals.
Unlikely Related	AE occurring with a reasonable time sequence to administration of the drug, but which could also be explained by concurrent disease or other drugs or chemicals.
Not Related	AE with a temporal relationship to drug administration which makes a causal relationship improbable, and in which other drugs, chemicals or underlying disease provide plausible explanations.

*Definitions with basis in *Clinical Data Acquisition Standards Harmonization (CDASH), ICH E2B*.

For data analysis and SAE reporting purposes, any AEs classified as 'unlikely related' will be regarded as 'not related' to study drug. AEs classified as 'possibly related' will be regarded as 'related' to the study drug.

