15.1 Adverse Events

An AE is any untoward medical occurrence in a subject or clinical investigation subject administered a pharmaceutical product that does not necessarily have a causal relationship with this treatment. An AE can therefore be any unfavorable and unintended sign (including a clinically significant abnormal laboratory finding), symptom or disease temporally associated with the use of a pharmaceutical product, whether or not considered related to the pharmaceutical product. AEs may include the onset of new illness and the exacerbation of pre-existing conditions.

For the purposes of this protocol, an AE is any undesirable sign(s), symptom(s) or worsening of pre-existing condition(s) occurring after the signing of the informed consent through the final study visit, even if the event is not considered to be related to the study drug. No AEs information will be collected following the Safety Follow-Up Visit. The nature of each AE, date of onset, outcome, severity, actions taken with respect to dosage, and relationship to study drug will be assessed and recorded.

An AE is “unexpected” when the nature, severity, specificity, or outcome is not consistent with the term or description used in protocol related documents including the Investigator brochure, product labeling

(e.g. Package Insert or Summary of Product Characteristics), protocol and Independent Ethics Committee (IEC)/ Institutional Review Board (IRB) approved informed consent form. If an Investigator is uncertain whether an AE is expected or unexpected, the AE should be reported as unexpected.

The outcome of each AE should be assessed as follows:

- Fatal: Subject has died due to AE
- Not Recovered/Not Resolved: AE is ongoing
- Recovered/Resolved: AE is no longer present
- Recovered/Resolved with sequelae: AE has resolved but the subject retains a condition that is the consequence of the AE
- Recovered/Resolving: AE is in the process of recovering
- Unknown: Outcome of the AE is not known because the subject did not return for follow-up and attempts to obtain follow-up were unsuccessful

The causality of each AE, with respect to each study drug separately, should be assessed using one of the following terms:

- Related: AE occurring in a plausible time relationship to drug administration, and which cannot be explained by concurrent disease or other drugs or chemicals.

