- Possibly Related: AE occurring with a reasonable time sequence to administration of the drug, unlikely to be attributed to concurrent disease or other drugs or chemicals.
- Unlikely Related: AE occurring with a reasonable time sequence to administration of the drug, but which could also be explained by concurrent disease or other drugs or chemicals.
- Not Related: AE with a temporal relationship to drug administration which makes a causal relationship improbable, and in which other drugs, chemicals or underlying disease provide plausible explanations.

For data analysis and Serious Adverse Event (SAE) reporting purposes, any AEs classified as 'unlikely related' will be regarded as 'not related' to study drug. AEs classified as 'possibly related' will be regarded as 'related' to the study drug.

The severity of all AEs should be graded in accordance with the NCI-CTCAE Version 4:

- 1 – Mild: Does not hamper daily activities
- 2 – Moderate: Hampers daily activities

3 – Severe: Makes daily activities impossible

4 – Life-Threatening: Imminent risk of death

5 – Death

Disease progression or symptoms related to disease progression will not be considered AEs.

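### No level that Table 14 counts as related fits an event with two credible causes, so the mandatory Grade 3+ stop can fail in TP1, the two stop rules can disagree in TP2, and some late non-fatal SAEs need not be reported

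*Protocol*

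**What the plan says.** **Stop rules.** Protocol 3.6 lists, among the reasons to end treatment, a Grade 3 or higher AE that "is observed and is determined to be related to either the Sodium Cridanimod or progestin therapy". Protocol 5.1.2 has a second rule, for combination therapy only: stop when such an AE "is observed and determined to be potentially related to either medication". SAP 5.3 repeats the 5.1.2 wording.

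**Causality scale.** Protocol 5.9.3, Table 14, has four levels. *Related* needs plausible timing and an event "which cannot be explained by concurrent disease or other drugs or chemicals". *Possibly Related* is an "AE occurring with a reasonable time sequence to administration of the drug, unlikely to be attributed to concurrent disease or other drugs or chemicals". The next level down, *Unlikely Related*, is an event "with a reasonable time sequence to administration of the drug, but which could also be explained by concurrent disease or other drugs". *Not Related* is for events whose timing makes a causal link improbable and which have another plausible explanation. For data analysis and SAE reporting, "any AEs classified as 'unlikely related' will be regarded as 'not related' to study drug", and *Possibly Related* counts as related. SAP 15.1 repeats the scale and the two-way collapse, and adds: "The causality of each AE, with respect to each study drug separately, should be assessed using one of the following terms".

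**Late reporting.** Under Protocol 5.9.1, AE collection ends at the End of Study or Safety Follow-up Visit. Under 5.9.5, an SAE up to 60 days after the last dose is reported if the investigator suspects a causal link. SAEs before the final visit are reported whatever their cause, and 5.9.6 requires every death during the study to be reported whatever its cause.

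**The concern.** A causality scale used for stopping and reporting should place an event that the drug may well have caused on the related side, even when something else may also have caused it. Here the dividing line falls elsewhere. A credible alternative is enough to move the event to the side that counts as not related, however plausible the drug is. In recurrent or persistent cancer, a credible alternative will often be at hand.

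Three things are at stake: a mandatory stop that may not apply in Treatment Period 1 (TP1), two stop rules that can give different answers for one subject in Treatment Period 2 (TP2), and late non-fatal SAEs that need not be reported. There is no control arm against which to judge attribution afterwards.

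**Working it through.** No sample-size or error-rate calculation applies. The check follows one kind of event through the rules: Grade 3 or higher, reasonable timing, with the drug and either the disease or another drug both credible causes.

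**Step 1: rating.**

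| Table 14 level | What it asks of the other cause | Fits the event? | Counts as |
|---|---|---|---|
| Related | must be excluded | No | related |
| Possibly Related | must be unlikely | No | related |
| Unlikely Related | could also explain the event | Yes | not related |
| Not Related | plausible, and timing makes the drug improbable | No, timing is reasonable | not related |

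Only *Unlikely Related* fits. SAP 15.1 uses the same test ("but which could also be explained by concurrent disease or other drugs or chemicals"), so the SAP does not correct it.

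**Step 2: stopping in TP1.** Protocol 5.1.2 is limited to combination therapy, so 3.6 is the only Grade 3+ causality stop for subjects on megestrol alone. An event rated *Unlikely Related* has not been determined to be related. This does not depend on the collapse rule, which names analysis and SAE reporting but not stopping.

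Protocol 1.3.1 lists pulmonary embolism among megestrol's reported reactions. If the cancer could also explain a non-fatal embolism (a clinical assumption), that event does not trigger the mandatory stop.

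**Step 3: stopping in TP2.** Both 3.6 and 5.1.2 apply. The 5.1.2 term, potentially related, is not a Table 14 level, and in plain English it can include the event. The same subject can then meet the stop in 5.1.2 and not the one in 3.6. Protocol 8.1.6 requires sponsor notification when a subject who developed withdrawal criteria was not withdrawn, so whether continuing is a deviation depends on which section is read.

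**Step 4: late SAEs.**
- Reporting limit: 60 days after last dose (5.9.5).
- TP2 Safety Follow-up Visit: 4 weeks = 28 days after last treatment, ± 3 days (5.4.3).
- Window in which reporting rests on suspected causality: 60 − 28 = 32 days. With the visit window it runs from 60 − 31 = 29 to 60 − 25 = 35 days.
- Subjects who leave at the end of TP1 normally take megestrol until the End of Study Visit (5.4.2), so their window is about 60 − 0 = 60 days.

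Because the collapse rule expressly covers SAE reporting, a non-fatal SAE in this window rated *Unlikely Related* need not be reported.

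**The case against.** The strongest reply is that little is lost in practice, and several parts of it stand.

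- **The mandatory stop is not lost throughout the trial.** A reader might infer that it is. In TP2 the broader rule in 5.1.2 also applies, and a cautious investigator would follow it. The clear gap is in TP1. Even there, 3.6 allows stopping for unacceptable AEs, concurrent illness or investigator judgment.
- **Fatal events do not drop out in the same way.** A reader might infer that they do. Protocol 5.9.6 captures deaths during the study regardless of cause, TP2 subjects have 12 months of survival follow-up, and the SAP keeps a mortality listing.
- **No numerical bias follows.** It is tempting to say that related events are undercounted by some factor. The SAP plans AE listings and no count of related events, and the documents give no share of events with two causes.
- **Related to neither drug is a strained reading.** Because SAP 15.1 rates each study drug separately, each could literally serve as the other drug for its partner. Protocol 4.1 groups cridanimod, megestrol and lidocaine as study drugs, so *other drugs* more naturally means non-study drugs. The literal reading is not excluded, and one sentence would close it.
- **Nothing shows that the listings hide the recorded term.** SAP 15.3 lists relatedness without saying whether it is the four-level term or the collapsed value.
- **The late-SAE trigger is suspicion, not a Table 14 level.** An investigator may still suspect causality after choosing *Unlikely Related*. The event is then reportable, but the scale points the other way.

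None of this supplies a related level for an event with two credible causes, or reconciles 3.6 with 5.1.2.

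**Conclusion.** The point holds, as a minor one. It is a definite fault in a stated rule, since the text assigns these events to the wrong side. The clear consequence is in TP1, where the only Grade 3+ causality stop does not reach them. In TP2 the consequence is two rules that can conflict. For late reporting it is a window of about 32 days after the TP2 Safety Follow-up Visit in which a non-fatal SAE at this rating need not be reported.

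The conclusion assumes that investigators apply Table 14 as written and that events with two credible causes occur in this population. How many subjects are affected cannot be derived: SAP 4.5 gives 25 women enrolled at closing, and neither document gives AE counts. No planned efficacy result is affected.

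**What to change.** 1. In Table 14 and SAP 15.1, define *Possibly Related* as a reasonable time sequence in which the drug cannot be ruled out, even if disease or other drugs could also explain the event. Keep *Unlikely Related* for events where timing or other evidence makes the drug improbable.
2. State that the partner study drug and lidocaine are not other drugs for this purpose.
3. Use one trigger, Related or Possibly Related per Table 14, in Protocol 3.6, Protocol 5.1.2 and SAP 5.3.
4. Apply the changes prospectively, without reclassifying past deviations.

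**Cost.** Some additional mandatory stops, which 5.1.2 already contemplates for TP2, and an amendment with IEC/IRB approval under Protocol 8.3.3, because subject safety is affected. The study is closing early, so this is worth doing only if subjects remain on treatment or the protocol is reused.

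**Optional clarification.** SAP 15.3 could say that the AE listings print the investigator's four-level causality term for each drug. That needs no new analysis.

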3.7. Patient Requirements

The following patient requirements apply from screening through completion or withdrawal of the study:

- Patients must have the availability to attend visits according to the protocol;
- Patients must not participate in any other clinical study;
- Patients of childbearing potential must use highly effective barrier contraception;
- Patients must keep a diary of megestrol acetate doses as described in Section 5.7.7.

3.8. Subject Identification

Subjects in this study will be identified only by the subject number (CCC-SS-XX), which consists of a 3-digit country code (CCC), a 2-digit site number (SS) followed by 2-digit consecutive enrollment number (XX) of subjects enrolled at the specific clinical site.

4. STUDY DRUG

4.1. Description of Study Drugs

For the most recent, detailed pharmaceutical information on Sodium Cridanimod and megestrol acetate, refer to the Sodium Cridanimod Investigator's Brochure and the Prescribing Information for megestrol acetate.

4.1.1 Sodium Cridanimod is a synthetic interferon inducer that has been extensively studied and is approved for many indications (mainly viral infections) in the Russian Federation and other Eastern European countries. Sodium Cridanimod (125 mg/mL) will be supplied to the investigational sites as a ready-to-use solution in ampules. One ampoule contains 2 mL, or 250 mg, of Sodium Cridanimod.

4.1.2 Megestrol acetate is a synthetic derivative of the naturally occurring hormone progesterone and is FDA approved for the treatment of advanced endometrial cancer. Megestrol acetate will be supplied in tablet form in doses of either 40 or 160 mg (depending on approved dosage forms in the applicable country).

4.1.3 Lidocaine Hydrochloride is a local anesthetic that is commonly used in clinical settings. It will be provided by the Investigator's pharmacy as a 2% (w/v) aqueous solution. As described in detail below, lidocaine will be mixed with Sodium Cridanimod to increase tolerability of the intramuscular injection.

4.2. Preparation of Sodium Cridanimod

To administer Sodium Cridanimod, the contents of 2 ampules (4 mL of solution equal to 500 mg of Sodium Cridanimod) and 1 mL of 2% lidocaine hydrochloride solution (for a total administration volume of 5 mL) should be withdrawn with a syringe. After the contents of the syringe are mixed, and all air

and air bubbles are removed from the syringe, the resulting solution is administered intramuscularly. It is preferable to rotate injection sites with each dose.

4.3. Study Drug Handling

Sodium Cridanimod may be requested by the Principal Investigator (or authorized designee) at each participating institution and will be shipped directly to the institution where the subject is to be treated.

The Investigator/pharmacist is responsible for safe and proper handling and storage of the study drugs at the investigational site. The study drugs must be stored in a secure area. Access to and administration of study drugs will be limited to the Investigator and authorized site personnel. The Investigator must ensure that study drugs are administered or dispensed only to subjects enrolled in this study and in accordance with the protocol. The study drugs must be stored at room temperature. Temperature logs should be kept updated by the Investigator, pharmacist or designated site personnel to document adequate storage during the course of the study.

It is the responsibility of the Investigator or, if applicable, pharmacist or designated site personnel to ensure that records of receipt, use by each subject, return, loss, or other disposition of study drugs are maintained at each study site. These records will include dates, quantities, batch numbers, and the unique subject numbers assigned to subjects. The Investigator must maintain records documenting that the subjects were provided with the doses specified in the protocol. Furthermore, they should reconcile all study drugs received from the Sponsor. It is the responsibility of the Investigator to give reasons for any discrepancies in study drug accountability and inventory. Study related forms and logs will be provided by the Sponsor to enhance drug accountability and inventory. All remaining study drugs shall be collected and disposed of according to the Sponsor's directions at the end of the study.

